03 SEP 2019, VERSION: 1.1

thrombosis or embolization and no test article was identified at defect sites or presumed sites of article migration. The test article provided excellent Hemostatic performance and had similar tissue response and similar adhesion incidence and severity as the control article, and had no detected adverse systemic effects (no thrombosis or particle embolization).

8.1. Comparison with Other Hemostatic Powders

SURGICEL Powder was compared with other commercially available hemostatic powder products in two in vivo models. Hemostatic efficacy of SURGICEL Powder was compared with two polysaccharide-based hemostats in a porcine liver punch biopsy model and with three polysaccharide-based hemostats and one non-regenerated oxidized cellulose hemostat in a porcine liver abrasion model. SURGICEL Powder provided more effective hemostasis (defined as hemostasis within 10 minutes of application), and faster time-to-hemostasis TTH than the other marketed hemostatic powders. The results from this in vivo study suggest that SURGICEL Powder may be useful in clinical applications where control of oozing capillary, mild venous, and small arterial hemorrhage is required, including bleeding in difficult-to-access locations.

9. INDICATIONS AND CONTRAINDICATIONS, PRECAUTIONS

9.1. Indication

SURGICEL Powder is used adjunctively in surgical procedures to assist in the control of capillary, venous, and small arterial hemorrhage when ligation or other conventional methods of control are impractical or ineffective.

9.2. Contraindications

All hazards associated with the use of SURGICEL Powder have been identified and appropriately mitigated.

This product should only be used by clinicians and staff properly trained in the use of the technology and its associated warnings and cautions.

SURGICEL Powder:

- Do not inject or place SURGICEL Powder into an open blood vessel. Do not use to treat bleeding from large defects in arteries or veins.
- SURGICEL Powder should not be used to control hemorrhage from large arteries or veins.

Confidential Page 38 of 86

- The SURGICEL Powder device was not designed for intraluminal procedures.
- When SURGICEL Powder is used to help achieve hemostasis in, around, or in
 proximity to foramina in bone, areas of bony confine, the spinal cord, or the optic
 nerve and chiasm, it must always be removed after hemostasis is achieved since it
 will swell and could exert unwanted pressure. Unlike other SURGICEL products,
 SURGICEL Powder cannot be removed from blood clots and complete removal
 of the device application may disrupt the clot and increase the risk of re-bleeding.
- SURGICEL Powder should not be used for implantation in bone defects, such as fractures, since there is a possibility of interference with callus formation and a theoretical chance of cyst formation.
- SURGICEL Powder should not be used on non-hemorrhagic serous oozing surfaces, since body fluids other than whole blood, such as serum, do not react with SURGICEL Powder to produce satisfactory hemostatic effect.
- SURGICEL Powder is an absorbable hemostat, and should not be used as an adhesion prevention product.

SURGICEL Endoscopic Applicator

- Do not inject or place SURGICEL Powder into an open blood vessel. Do not use to treat bleeding from large defects in arteries or veins.
- SURGICEL Powder should not be used to control hemorrhage from large arteries or veins.
- The SURGICEL Endoscopic Applicator was not designed for intraluminal procedures.

9.3. Warnings and Precautions

- SURGICEL Powder is not intended for use on dry (non-bleeding) surfaces or for prevention of bleeding.
- SURGICEL Powder is supplied sterile and as the material is not compatible with autoclaving or ethylene oxide sterilization, SURGICEL Powder should not be resterilized.
- SURGICEL Powder is not intended as a substitute for careful surgery and the proper use of sutures and ligatures.
- Closing with SURGICEL Powder in a contaminated wound without drainage may lead to complications and should be avoided.

Confidential Page 39 of 86

- The hemostatic effect of SURGICEL Powder is greater when it is applied dry; therefore, it should not be moistened with water or saline prior to application.
- SURGICEL Powder should not be impregnated with anti-infective agents or with other materials such as buffering or hemostatic substances. Its hemostatic effect is not enhanced by the addition of thrombin, the activity of which is destroyed by the low pH of the product.
- Although SURGICEL Powder may be left in situ when necessary, it is recommended to remove excess powder with irrigation and aspiration once hemostasis is achieved, without disturbing the clot.
- SURGICEL Powder is dry and there may be difficulties in precise delivery under certain circumstances. Unintentional device placement may result in powder scattering and device migration that may increase the risk of adhesion formation. In preclinical in vivo animal studies it was demonstrated that SURGICEL Powder does not increase the incidence of remote adhesions in laparoscopic procedures.
- Dislodgement of SURGICEL Powder could possibly occur by intraoperative manipulation, lavage, exaggerated respiration, etc. With other SURGICEL products, there have been reports that in procedures such as lobectomy, laminectomy, and repair of a frontal skull fracture and lacerated lobe, when the product was left in the subject after closure it migrated from the site of application into foramina in bone around the spinal cord, resulting in paralysis and, in one case, the product migrated into the left orbit of the eye, causing blindness. While these reports cannot be confirmed to be related to SURGICEL products, special care must be taken by physicians, regardless of the type of surgical procedure. Consider removing SURGICEL Powder in these applications (procedures) after hemostasis is achieved.
- Although SURGICEL Powder is bactericidal against a wide range of pathogenic microorganisms, it is not intended as a substitute for systemically administered therapeutic or prophylactic antimicrobial agents to control or to prevent postoperative infections.
- Do not resterilize/reuse. Reuse of this device (or portions of this device) may create a risk of product degradation, which may result in device failure and/or cross-contamination, which may lead to infection or transmission of blood-borne pathogens to patients and users.
- Do not attempt to trim the applicator tip.

Confidential Page 40 of 86

03 SEP 2019, VERSION: 1.1

- SURGICEL Powder should not be used in conjunction with autologous blood salvage circuits, because its fragments may pass through the transfusion filters of blood-scavenging systems.
- Use only as much SURGICEL Powder (oxidized regenerated cellulose) as is necessary and apply only where needed for hemostasis. Remove any excess before surgical closure in order to facilitate absorption and to minimize the possibility of foreign body reaction.
- Use minimal amount of SURGICEL Powder required to achieve hemostasis, and remove excess powder in the area of drains to prevent clogging. In urological procedures, minimal amounts of SURGICEL Powder should be used and care must be exercised to prevent plugging of the urethra, ureter, or a catheter by dislodged portions of the product.
- Since absorption of SURGICEL Powder could be prevented in chemically cauterized areas, its use should not be preceded by application of silver nitrate or any other escharotic chemicals.
- If SURGICEL Powder is used temporarily to line the cavity of open wounds, it should be removed by irrigation with sterile water or saline solution after bleeding has stopped.
- Precautions should be taken in otorhinolaryngologic surgery to ensure that none of the material is aspirated by the subject (e.g., controlling hemorrhage after tonsillectomy and controlling epistaxis).
- The applicator tip provided on the SURGICEL Powder device is not intended for laparoscopic or other endoscopic use. If laparoscopic or other endoscopic use is desired, remove the existing applicator tip from the SURGICEL Powder device, and replace with the SURGICEL Endoscopic Applicator tip (supplied separately). In laparoscopic or other endoscopic procedures, SURGICEL Powder should only be applied using the SURGICEL Endoscopic Applicator. Consult the SURGICEL Endoscopic Applicator Instructions for Use (IFU) for proper assembly and directions for use with the SURGICEL Powder device.

SURGICEL Endoscopic Applicator

- The SURGICEL Endoscopic Applicator is supplied sterile and as the material is not compatible with autoclaving or ethylene oxide sterilization, the SURGICEL Endoscopic Applicator should not be resterilized.
- To prevent clogging, do not touch the tip to wet surface. Be careful to avoid damaging tissue with the rigid tip.

Confidential Page 41 of 86

- Do not attempt to trim the applicator tip. Replace the tip if it becomes clogged.
- Do not use the SURGICEL Endoscopic Applicator if package is opened or damaged.
- Apply SURGICEL Powder according to the product's labeling.
- Do not resterilize/reuse. Reuse of this device (or portions of this device) may create a risk of product degradation, which may result in device failure and/or cross-contamination, which may lead to infection or transmission of blood-borne pathogens to patients and users.
- The SURGICEL Endoscopic Applicator is supplied with a flexible inner tip inside a rigid cannula. The rigid cannula cannot be used independently.
- The SURGICEL Endoscopic Applicator should only be used by persons having adequate training and familiarity with endoscopic techniques. Consult medical literature relative to techniques, complications, and hazards prior to performance of any endoscopic procedure.
- After use, dispose of the SURGICEL Endoscopic Applicator in accordance with biohazardous material protocol.

10. OVERALL DESIGN

10.1. Trial Design

This is a single blind, prospective, randomized, multicenter, multispecialty, controlled clinical study comparing SURGICEL Powder with SURGICEL Original as an adjunct to achieve hemostasis in the control of capillary, venous, and small arterial hemorrhage when ligation or other conventional methods of control are impractical or ineffective during surgery (open, laparoscopic or thoracoscopic) in Chinese adult (≥18 years old) subjects.

At least 234 evaluable subjects with an appropriate mild or moderate TBS will be randomized in a 1:1 allocation ratio to either SURGICEL Powder or SURGICEL Original (control).

After application of either SURGICEL Powder or SURGICEL Original, the TBS will be assessed for hemostasis (no detectable bleeding) at 3, 5, and 10 minutes from application and prior to initiation of final fascial closure on open surgery or port site closure in laparoscopic or thoracoscopic procedures.

All enrolled subjects will be followed post-operatively through discharge, and via phone call or office visit at 30 days (+14 days) post-surgery. In addition, all enrolled subjects

Confidential Page 42 of 86

ETHICON, LLC. BIOS_2017_02

03 SEP 2019, VERSION: 1.1

will receive a 6-month (+/-30 days) follow-up phone call or office visit to assess the occurrence of any SAE requiring surgical intervention and assessed as possibly related or related to the study treatment.

10.1.1. Trial Objective

The objectives of this study are to evaluate the safety and to demonstrate non-inferiority of hemostatic effectiveness of SURGICEL Powder compared with SURGICEL Original in controlling mild or moderate parenchymal or soft tissue intraoperative bleeding during general, gynecological, and cardiothoracic surgery of Chinese adult (≥18 years old) subjects.

10.1.2. Trial Method Selection and Its Rationale

This is a single blind, prospective, randomized, controlled clinical study. Prospective subjects will be informed about the nature of the research, given the informed consent form (ICF) to read, and, if he/she understands the content, will be asked to provide consent by signing the ICF.

The Investigator is expected to invite all subjects expected to meet the study entry criteria to participate in the study.

10.1.3. Measures to Reduce and Avoid Bias

Randomization will be used to avoid bias in the assignment of treatment to each subject, to increase the likelihood that attributes of the subject are evenly balanced across treatment groups, and to enhance the validity of statistical comparisons across treatment groups.

The study related data will be recorded in the original Medical Records and reviewed during the monitoring process. Proper training for the investigators will be planned to ensure all investigators have equal and adequate experience with the device prior to commencing enrollment at their site.

10.1.4. Trial Endpoints

Primary Effectiveness Endpoint

 Proportion of subjects achieving hemostatic success at 5 minutes following the application of SURGICEL Powder or SURGICEL Original with no re-bleeding requiring additional treatment at the TBS any time prior to initiation of final fascial closure.

Secondary Effectiveness Endpoints

Confidential Page 43 of 86

- Proportion of subjects achieving hemostatic success at 3 minutes following the
 application of SURGICEL Powder or SURGICEL Original with no re-bleeding
 requiring additional treatment at the TBS any time prior to initiation of final
 fascial closure.
- Proportion of subjects achieving hemostatic success at 10 minutes following the application of SURGICEL Powder or SURGICEL Original with no re-bleeding requiring additional treatment at the TBS any time prior to initiation of final fascial closure.

Safety Endpoints

- Incidence of thromboembolic events that were assessed as possibly related or related to the study treatment (from enrollment through the 30-day follow-up phone call or office visit);
- Incidence of post-operative re-bleeding that was assessed as possibly related or related to the TBS and requiring medical/surgical intervention (from initiation of final fascial closure through the 30-day follow-up phone call or office visit);
- Incidence of SAEs requiring surgical intervention and assessed as possibly related or related to the study treatment (from enrollment through the 6-month follow-up phone call or office visit)

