10.1.13. Safety Evaluation Method

Description of safety parameters

The safety parameters in this study are the following:

- Incidence of thromboembolic events that were assessed as possibly related or related to the study treatment (from enrollment through the 30-day follow-up phone call or office visit);
- Incidence of post-operative re-bleeding that was assessed as possibly related or related to the TBS and requiring medical/surgical intervention (from initiation of final fascial closure through the 30-day follow-up phone call or office visit);
- Incidence of serious adverse events requiring surgical intervention and assessed as possibly related or related to the study treatment (from enrollment through the 6-month follow-up phone call or office visit)

Selection of method and time to evaluate, record, and analyze the safety parameters

Subjects will be assessed for all AEs and SAEs from time of ICF through the 30-day follow-up. At the 6-month follow-up, only SAEs requiring surgical intervention and assessed as possibly related or related to the study treatment, will be reported. The safety

Confidential Page 49 of 86

parameters are recorded on the e-CRF according to the Investigator's record, medical record, and all other related source documents, which are collected at each follow-up visit.

Sponsor's Medical Director (Study Medical Monitor/Safety Lead) will assess all serious adverse events for causality and expectedness and will utilize Ethicon's Product Safety Committee (PSC) to review and adjudicate the following safety signals:

- Thromboembolic events
- Postoperative re-bleeding
- Reoperations for complications assessed as possibly related or related to the study treatment

The PSC will also review cumulative safety data from the study. The PSC will advise on the continuing safety of study subjects and those yet to be recruited to the study. Based on cumulative data from the study, the PSC may recommend whether to continue, suspend, modify, or stop the study. At the conclusion of the study, the PSC will also give a final assessment of the safety of the product from this study. The composition, responsibilities, frequency of PSC meetings, handling of emergency situations, and documentation of PSC meetings will be specified in the Safety Management Plan (SMP).

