11.3.6. Randomization Procedure

Randomization will be stratified by investigational site and bleeding severity: mild or moderate bleeding. Sponsor will provide each site with computer-generated randomization envelopes, each bearing the subject randomization number, and containing the treatment allocation and stratification.

The identified TBS will be treated after stratification and randomization, based on the procedures described in this protocol. Treatment will be assigned randomly to each subject on a 1:1 basis to SURGICEL Powder or SURGICEL Original. If a potential subject fails intra-operative criteria (i.e., no TBS identified, or has an intra-operative exclusion), and is not enrolled in the study, the unused randomization envelope should be returned to the series, and used for the next subject.

This will be a single blinded study where the subject will be blinded to treatment. Subjects should remain blinded throughout the trial. Given the differences in appearance

Confidential Page 54 of 86

of the two treatment groups, it will not be possible for the Investigator to be blinded to the treatment. However, to avoid any bias in the conduct of the surgical procedure, randomization should only take place after completion of the following steps:

- 1. SURGICEL Powder and SURGICEL Original will be available in the operating room for administration for each subject.
- 2. The Investigator must perform the surgical procedure according to his/her standard of care.
- 3. When the Investigator encounters the first appropriate TBS related to the primary operative procedure that requires an adjunct to achieve hemostasis because traditional methods have been determined to be ineffective or impractical, he/she should classify the severity of bleeding to be treated.
- 4. The subject will then be randomized immediately by opening the appropriate randomization envelope, based on stratification of bleeding severity.
- 5. The randomly assigned treatment article (SURGICEL Powder or SURGICEL Original) will be applied to the TBS immediately, per the IFU/IB of each product.

The subject will remain blinded to treatment throughout the study.

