7. STATISTICAL CONSIDERATIONS

For the primary or secondary effectiveness endpoints, the analyses based on the ITT set will consider missing data as failures. Missing data for safety endpoints will not be imputed.

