14. SAFETY OUTCOMES

14.1. . SAFETY ENDPOINTS

The following safety endpoints will be included in this study:

- Incidence of thromboembolic events that were assessed as possibly related, probably related, or related to the study treatment (from enrollment through the 30-day follow-up phone call or office visit):
- Incidence of post-operative re-bleeding that was assessed as possibly related, probably related, or related to the study treatment and requiring medical/surgical intervention (from initiation of final fascial closure through the 30-day follow-up phone call or office visit);
- Incidence of SAEs requiring surgical intervention and assessed as possibly related, probably related, or related to the study treatment (from enrollment through the 6-month follow-up phone call or office visit).

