14.2. ADVERSE EVENT

For this study, an AE is defined as an untoward medical occurrence (sign, symptom or disease) in a subject or clinical trial subject and which does not necessarily have a causal relationship with the study medical device. An untoward medical occurrence includes any new, undesirable medical experience or worsening of a pre-existing condition.

Enrollment through the 30-Day Follow-Up: All AEs, whether attributable to the device/procedure or not, are to be recorded in the eCRF and reported to the Sponsor.

If a subject reports the same AE more than once within that SOC/PT, the AE with the worst-case relationship to study medication will be used in the corresponding relationship summaries.

Adverse events will be coded using Medical Dictionary for Regulatory Activities (MedDRA) version 21.1 as defined in the Data Management Plan.

Incidence for the following adverse events will be summarized by system organ class, preferred term and treatment based on the safety analysis set. Subjects are counted only once within each system organ class and each preferred term.

- •All serious adverse events.
- •All adverse events.
- •All adverse events by maximum severity in the following order: severe, moderate and mild (if severity is missing, the adverse event will be considered as severe for summary tables and will be presented in the data listing with a missing severity)
- All adverse events by strongest relationship to study device in the following order: Related, Probably Related, Possibly Related, Unlikely Related, Not Related (the relationship to study drug will be determined by investigators). If causality is missing, the adverse event will be considered probably related for summary tables, but will be presented in the data listing with a missing relationship.
- •All adverse events leading to discontinuation of study treatment.

All adverse events, serious adverse events, deaths, and adverse events leading to discontinuation of study device will be listed in by-subject listings separately.

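### All three safety endpoints count only events judged related, starting from an unblinded assessment, and no all-cause versions by arm are planned

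*Protocol*

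**What the plan says.** Protocol 10.1.4 defines three safety endpoints, each with a relatedness filter:

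- Thromboembolic events to day 30: "Incidence of thromboembolic events that were assessed as possibly related" or related to the study treatment.
- Post-operative re-bleeding needing intervention, to day 30: "Incidence of post-operative re-bleeding that was assessed as possibly related" or related to the TBS.
- Surgical SAEs to 6 months: "Incidence of SAEs requiring surgical intervention and assessed as possibly related or related to the study treatment".

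SAP 14.1 keeps the filters and changes the second one to "post-operative re-bleeding that was assessed as possibly related, probably related, or related to the study treatment and requiring medical/surgical intervention". SAP 14.7 presents this as a clarification.

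Protocol 19.5 and SAP 14.2 give the relatedness judgement to the investigator. Of that person Protocol 11.3.6 says "it will not be possible for the Investigator to be blinded to the treatment". Protocol 10.1.6 and 10.1.13 add a second layer. The sponsor's Medical Director assesses all SAEs for causality. The sponsor's Product Safety Committee (PSC) adjudicates thromboembolic events, post-operative re-bleeding and reoperations assessed as related.

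To day 30, all adverse events are recorded whatever their cause (Protocol 19.2.2, 19.6) and tabulated by system organ class, preferred term and arm (SAP 14.1.1, 14.2). After that, Protocol 10.1.13 says: "At the 6-month follow-up, only SAEs requiring surgical intervention and assessed as possibly related or related to the study treatment, will be reported".

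On missing values, SAP 7 says "Missing data for safety endpoints will not be imputed", while SAP 14.2 says "If causality is missing, the adverse event will be considered probably related for summary tables". Protocol 13.2 plans no inferential statistics for safety.

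**The concern.** A randomised control arm lets event rates be compared without deciding what caused each event. An endpoint restricted to related events puts that decision back into the comparison. Here the first person to decide knows the arm, and according to Protocol 7 no clinical investigation of SURGICEL Powder preceded this trial, so there is little clinical experience to guide the call. The bias could go either way: a new product may attract more attributions, or events may be put down to the operation.

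The SAP's change to the re-bleeding endpoint makes the filter stronger. Whether a bleed came from the TBS is largely a question of location; whether it was related to the study treatment is a causal question. A TBS re-bleed attributed to the surgery would meet the protocol's definition but not the SAP's.

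At stake is how the named safety endpoints read by arm in a registration trial. For new surgical SAEs after the 30-day visit, an all-cause comparison could not be rebuilt later.

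**Working it through.** **The plan's own figures.** The documents give no sample size, power or precision for any safety endpoint. The only design calculation is for the primary endpoint, and it reproduces. With success rates 0.85 and 0.80, margin 0.10, one-sided 0.025 and 80% power, the Farrington-Manning formula gives 104.1, hence 105 per arm, with asymptotic power 80.3% at 105. Then 105 / 0.90 = 116.7, hence 117 per arm and 234 in total. This point does not affect those figures; 117 is used below as the arm size.

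**How the filter acts.** Let n be the arm size, r the all-cause risk and a the probability that an event is called related.

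- Expected counted events = n × r × a.
- Observed ratio, Powder to Original = (true risk ratio) × (a on Powder / a on Original).

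The true ratio is recovered only if a is the same in both arms.

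**Illustration.** The documents give no attribution probabilities and no all-cause rates for these endpoints, so all inputs are assumed. The 6.6% is the literature median for re-bleeding after SURGICEL in Protocol 7; it is borrowed only as an upper value, since it is not the same outcome. Assume equal true risk, with 25% of events called related on Powder and 50% on Original:

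| All-cause risk, both arms | All events per arm | Counted, Powder | Counted, Original |
|---|---|---|---|
| 2% | 2.3 | 0.6 | 1.2 |
| 5% | 5.9 | 1.5 | 2.9 |
| 6.6% | 7.7 | 1.9 | 3.9 |

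The observed ratio is 0.25 / 0.50 = 0.5 in every row. With the percentages reversed it is 2.0; with equal attribution it is 1.0.

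A second set of assumptions shows both errors:

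- No true difference: 3% in both arms, attribution 60% on Powder and 30% on Original. 3% × 60% = 1.8% and 3% × 30% = 0.9%, that is 117 × 0.018 = 2.1 against 117 × 0.009 = 1.1 subjects. The endpoint shows a doubling.
- A true doubling: 6% on Powder and 3% on Original, attribution 30% and 60%. 6% × 30% = 1.8% and 3% × 60% = 1.8%. The doubling is hidden.

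Counts this small mean that one or two attribution calls change the picture.

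**What the planned adverse event tables can replace.**

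- Thromboembolic events: all are recorded to day 30, but no group of preferred terms is defined, so the total is not displayed.
- Re-bleeding: a table by preferred term does not show whether the TBS was the source or whether intervention was needed.
- Surgical SAEs: a table by preferred term does not show which SAEs required surgery. New ones after the 30-day visit are absent unless judged related.

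**Sections that disagree.** Protocol 11.7 and footnote 8 of Table 1 follow all SAEs ongoing at day 30. Protocol 19.3 and 19.6 limit this to related ones. Protocol 10.1.13 filters 6-month reports on relation to the study treatment, and 19.6.1 on relation to the device or procedure.

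**The case against.** The strongest reply has four parts.

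First, a reader might infer that the investigator's word alone fixes the endpoints. The documents do not support that: the sponsor assesses causality for all SAEs, and the PSC adjudicates categories that closely match the three endpoints. This stands as a correction of scope. It does not remove the problem. The PSC is the sponsor's own committee, its blinding is not stated, and no section says whose call enters the endpoint. For reoperations it receives only those already assessed as related.

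Second, a reader might infer that these endpoints are the trial's only comparative safety statements. They are not: all adverse events and SAEs to day 30 are tabulated by arm, and haemoglobin and transfusion are also summarised by arm. Two of the three endpoints end at day 30, so their all-cause versions should be recoverable from data already planned. What is missing for them is the display.

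Third, a reader might infer that no SAE judged unrelated is followed after day 30. Protocol 11.7 and footnote 8 of Table 1 say otherwise for SAEs already ongoing, though other sections conflict. Only new SAEs are clearly lost. Both products are described as absorbed in about 2 weeks, so a narrow late check may be deliberate, although the protocol does not give that reason.

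Fourth, the two rules for missing relatedness might be read as a contradiction. They can also be read as a general rule and a specific one, with the specific, conservative rule governing. The SAP does not say that the specific rule extends to the endpoints in 14.1, so a clarifying sentence is enough.

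**Conclusion.** The concern holds in a limited form. The safety endpoints as defined depend on attribution that begins with an unblinded assessor. The status of the later review is unspecified, the SAP tightens the filter for re-bleeding, and no all-cause version of any of the three endpoints is planned. The loss that cannot be recovered is confined to new SAEs needing surgery, judged unrelated, after the 30-day visit.

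The distortion equals the ratio of attribution probabilities, which is unknown. The factor of two in either direction rests wholly on assumed probabilities, and the documents contain no evidence that attribution will in fact differ between arms. Safety is descriptive, so no error rate and no non-inferiority conclusion is affected; the harm is to the reading of the arm comparison. The change is worth making because it is cheap, not because the trial fails without it.

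**What to change.** 1. In SAP 14.1.1, add all-cause versions of the endpoints by arm beside the related versions: any thromboembolic event to day 30, with the preferred terms listed in advance; any post-operative re-bleed needing intervention to day 30, with TBS re-bleeds shown separately whatever their attribution to the product; and any SAE requiring surgical intervention. The TBS row still needs a judgement of location, which is why the any-re-bleed row should come first.
2. State that the missing-causality rule in SAP 14.2 also governs the endpoints in SAP 14.1.
3. State whose assessment defines each endpoint, and whether the sponsor and PSC reviews are blinded to arm.
4. At the existing 6-month contact, record every SAE requiring surgical intervention, with relatedness as a data field. SAP 14.7 describes the deviation assessment in the past tense, so these contacts may already be complete. If so, limit the all-cause SAE table to day 30 and report the later gap as a limitation.
5. Reconcile Protocol 11.7 and footnote 8 of Table 1 with 19.3 and 19.6 on ongoing SAEs, and 10.1.13 with 19.6.1 on the 6-month filter.

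Items 1 and 2 cost a few tables and a sentence, using data already collected to day 30. This assumes that the recorded action taken identifies surgery. Item 4 needs a small eCRF change and a protocol amendment. All-cause rates will look higher than the related ones, and the report should say why.
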